# 12.4. Confidentiality

All information generated in this study is considered highly confidential and must not be disclosed to any person or entity not directly involved with the study unless prior written consent is provided from the sponsor.

Prior to study participation, the Investigator shall inform the subject that the monitor(s), auditor(s), IRB/IEC, and the regulatory authorities will be granted direct access to the subject's original medical records for verification of clinical study procedures and/or data, and that, by signing a written ICF, the subject is authorizing such access.

In addition, prior to study participation, the subject must be informed that the records identifying the subject will not be made publicly available; if the results of the study are published, the subject's identity will remain confidential.

# 12.5. Protocol Compliance

The Investigator/institution will conduct the study in compliance with the protocol agreed to by the sponsor and regulatory authorities (if applicable) and that was approved by the IRB/IEC. The

Investigator/institution and the sponsor should sign the protocol, or an alternative contract, to confirm agreement.

The Investigator should not implement any deviation from, or changes to, the protocol without agreement by the sponsor and prior review and documented approval from the IRB/IEC of an amendment, except where necessary to eliminate immediate hazard(s) to study subjects or when the change involves only logistical or administrative aspects of the study (eg, change in monitor, change of telephone number).

When an important deviation from the protocol is deemed necessary for an individual subject, the Investigator must contact the Clinical Lead for the study. Such contact must be made as soon as possible to permit a review by the sponsor to determine the impact of the deviation on the subject's participation and/or the assessment of safety or efficacy in the study. Any significant protocol deviations affecting subject eligibility and/or safety must be reported by Investigator or site delegate to the IRB/IEC and regulatory authorities, as applicable, prior to implementation.

The Investigator should document and explain any deviation from the approved protocol.

# **13.** QUALITY CONTROL AND QUALITY ASSURANCE

Quality assurance and quality control systems shall be implemented and maintained with written SOPs to ensure that the study is conducted and data are generated, documented (recorded), and reported in compliance with the protocol, GCP, and the applicable regulatory requirement(s). Quality control shall be applied to each stage of data handling to ensure that all data are reliable and have been processed correctly.

An agreement must be secured from all involved parties to ensure direct access to all study-related sites, source documents, and reports for the purpose of monitoring and auditing by the sponsor and inspection by regulatory authorities.

# **13.1.** Training of Study Site Personnel

Prior to study activities being initiated at the study site, the sponsor or designee will train study site personnel on the protocol and applicable procedures. Training should be documented.

Note: If new study site personnel are assigned to the study after the initial training, study sites should contact the study monitor to coordinate training. Qualified study personnel may conduct training, as appropriate. Training of new study personnel should also be documented.

# 13.2. Monitoring

Study site monitoring is conducted to ensure the study is progressing as expected, the rights and well-being of human subjects are protected, the reported study data are accurate, complete, and verifiable, and the conduct of the study is in compliance with the currently approved protocol, with GCP and with applicable regulatory requirements. Protocol deviations identified will be documented.

Details of study site monitoring are documented in the study Clinical Monitoring Plan (CMP) or similar document. The CMP describes in detail who will conduct the monitoring, at what frequency monitoring will be done, at what level of detail monitoring will be performed (eg,

targeted and/or risk based), and the distribution of monitoring reports. Monitoring may include a study site selection visit, which may be conducted in person or via communication media (eg, teleconference, online meeting) or may be waived in accordance with policy and procedures being followed for the study, if appropriate. Monitoring will include a study site initiation visit, interim monitoring visit(s), and a study site closeout visit. An interim monitoring visit may be combined with a closeout visit, if applicable.

## 13.3. Audit

An audit of one or more participating study sites may be performed independently of, and separately from, routine monitoring to evaluate clinical study conduct and compliance with the protocol, SOPs, GCP, and the applicable regulatory requirements.

# 14. DATA HANDLING AND RECORD KEEPING

## 14.1. Data Management

## 14.1.1. Case Report Forms

An eCRF must be completed for each subject screened/enrolled in this study. These forms will be used to transmit information collected during the study to the sponsor and regulatory authorities, as applicable.

The documentation related to the validation of the eCRFs will be maintained in the Trial Master File (TMF). The TMF will be maintained by the CRO and the sponsor.

The Investigator will document subject data in his/her own subject files. These subject files will serve as source data for the study. All eCRF data required by this protocol will be recorded by study site personnel. All data entered into the eCRF will be supported by source documentation.

The Investigator or an authorized member of the Investigator's staff will make any necessary corrections to the eCRF. All changed information, including the date and person performing the corrections, will be available via the audit trail, which will be part of the electronic data capture system. For any correction, a reason for the alteration will be provided. The eCRFs will be reviewed periodically for completeness and acceptability by sponsor personnel (or their representatives). The sponsor (or their representatives) will also be allowed access to all source documents pertinent to the study in order to verify eCRF entries. The Investigator will review the eCRFs for completeness and accuracy and provide his or her electronic signature and date to the eCRFs as evidence thereof.

## 14.1.2. Source Documents

Per regulatory requirements, the Investigator or designee will maintain accurate and up-to-date study documentation, including source documentation for each study subject. Source documents are defined as original documents, data, and records. These may include, but are not limited to, hospital records, clinical and office charts, endoscopy reports, laboratory data/information, evaluation checklists, pharmacy dispensing and other records, recorded data from automated instruments, ECGs, X-rays, ultrasounds, RHC reports, ECHOs. Data collected during this study must be recorded on the appropriate source documents.

The Investigator(s)/institution(s) will permit study-related monitoring, audits, IRB/IEC review, and regulatory inspection(s) and will provide direct access to the source data.

# 14.2. Study Documentation and Records Retention

The Investigator and study staff have the responsibility of maintaining a comprehensive and centralized filing system containing all study-related documentation. These files must be available for inspection by the sponsor, representatives of the sponsor, the IRB/IEC, and regulatory authorities (ie, Food and Drug Administration [FDA] or international regulatory authorities) at any time, and should consist of the following elements:

- Subject files: Containing the completed eCRFs (if applicable), supporting source documentation including medical records, laboratory data, and signed ICFs.
- Regulatory files: Containing the protocol with all amendments and Investigator signature pages, copies of all other regulatory documentation, all correspondence between the study site and the IRB/IEC and sponsor, and drug accountability files, including a complete account of the receipt and disposition of the study treatment.

Records will be available for 2 years after marketing application approval, or if the application is not approved or never submitted, 2 years after the last shipment and delivery of the study treatment and the appropriate competent regulatory authorities are notified. The sponsor will provide written notification when it is appropriate for the Investigator to discard the study-specific documents referenced above.

During the record retention period, the Investigator or designee must inform the sponsor or designee (eg, CRO), of the following:

- Location of study documentation
- If the custody of documentation will be transferred or moved to another location
- If the Investigator is unable to retain documentation for the specified period

# 14.3. Clinical Study Report

Whether the study is completed or prematurely terminated, a clinical study report will be prepared and provided to the regulatory agencies according to applicable regulatory requirement(s).

# 14.4. Disclosure of Study Results

The sponsor will post the results of the study in a publicly accessible database in accordance with the applicable laws and regulations.

# **15. RESPONSIBILITIES**

# **15.1.** Investigator Responsibilities

The Investigator must comply with this protocol and the conduct of all study procedures. The Investigator will disclose to the sponsor sufficient, accurate, financial information to allow the

sponsor to submit accurate disclosure statements to the FDA per 21 Code of Federal Regulations (CFR) Part 54 (Financial Disclosure by Clinical Investigators) or to other regulatory authorities that have similar requirements. The Investigator is responsible for compliance with applicable sections of ICH GCP requirements. The investigator may also be responsible for compliance with 21 CFR Part 312, Subpart D, (*Responsibilities of Investigators*) and other, federal, and local laws, applicable to conducting drug studies.

The Investigator is responsible for ensuring an investigation is conducted according to the signed Investigator statement, the investigational plan, and applicable regulations; for protecting the rights, safety, and welfare of subjects under the Investigator's care; and for the control of drugs under investigation. An Investigator shall, in accordance with the provisions of ICH GCP guidelines and/or 21 CFR Part 50, obtain the informed consent of each human subject to whom the drug is administered.

# **15.2.** Sponsor Responsibilities

The sponsor is responsible for compliance with applicable sections of ICH Guideline E6(R2) and 21 CFR Part 312, Subpart D (*Responsibilities of Sponsors*). The sponsor is responsible for selecting qualified Investigators. Sponsors are also responsible for providing them with the information they need to conduct an investigation properly, and ensuring proper monitoring of the investigation(s). Sponsors are also responsible for ensuring the investigation(s) is conducted in accordance with the general investigational plan and protocols contained in the Investigational New Drug (IND) application (or equivalent), maintaining an effective IND (or equivalent) with respect to the investigations, and ensuring the FDA (and/or other regulatory authorities as applicable), and all participating Investigators are promptly informed of significant new adverse effects or risks with respect to the drug.

# **APPENDIX 1: SCHEDULE OF ASSESSMENTS**

## Table 4:

## Study APD418-201 Schedule of Assessments: Part A and Part B

Study Day	-21 to 1 (Part A) -14 to 1 (Part B) a						D	ay 1							Daj	y 2	Day 9 (± 2)
Study Period	Screen	Predose Period b	Baseline c			E	osing	Perio	d d		I	Postdo	se Peri	iod e ar	nd Dischar	rge f	Follow-Up g
Time from Initiation of Study Treatment (hours)	NA	> -2	-2 to 0	0.5	1	2	3	4	5	6 h /EEOI i	6.5	7	8	10	18 (+ 3 h)	24 (+ 6 h)	NA
Informed consent	Х																
Inclusion/Exclusion criteria	Х	Х	Х														
Demographics	Х																
Medical/surgical history	Х	Х															
Prior/concomitant medications	Х			•	•									•		•	X
Height and weight	Х	Xj										Xj				Xj	
Meals k		Х				Х											
Physical examination 	Х	Х														Х	
Vital signs m	Х	Х	Х	Х	Х	Х	Х	Х	Х	Х	Х	Х	Х	Х	Х	Х	
12-lead ECG n	Х	Х	Х	Х	Х	Х		Х		Х			Х		Х	Х	
ECHO o	Х		Х							Х			Х			Х	
RHC assessments p																	
Cardiac biomarkers q	Х	Х	Х		Х	Х		Х		Х			Х	Х	Х	Х	
Markers of renal function r	Х		Х			Х		Х		Х			Х	Х	X	Х	
Urine output s										1				•		Х	
DNA for genetic testing (optional)			Х														

Study Day	-21 to 1 (Part A) -14 to 1 (Part B) a						D	ay 1							Daj	y 2	Day 9 (± 2)
Study Period	Screen	Predose Period b	Baseline c			Ľ	osing	Perio	d d		]	Postdo	se Per	iod e an	d Discha	rge f	Follow-Up g
Time from Initiation of Study Treatment (hours)	NA	> -2	-2 to 0	0.5	1	2	3	4	5	6 h /EEOI i	6.5	7	8	10	18 (+ 3 h)	24 (+ 6 h)	NA
Hematology, serum chemistry, and coagulation	X t		Х							Х						Х	
Inflammation and endothelial biomarkers			Х							Х						Х	
Serum pregnancy test u	X t																
Urine pregnancy test u		Х															
Urinalysis	X t	Х								Х						Х	
Urine drug screen v		Х															
Randomization			Х														
Administer Study Tx w																	
PK blood sample x			Х	Х	X	X	Х	Х	Х	X	Х	Х	X	Х	Х	Х	
PK urine samples y					•	•		•	•				•				
Adverse events	Х		•														Х

a Screening period for Part A is up to 21 days prior to (and including) Day 1. Screening period for Part B is up to 14 days prior to (and including) Day 1.

b Predose assessments are performed on Day 1 prior to RHC insertion (Hours > -2), including certain assessments for confirmation of eligibility.

c Baseline assessments are performed over at least 2 hours from RHC insertion to start of study treatment administration (Hours –2 to 0), including confirmation of hemodynamic eligibility criteria and randomization, followed by all other assessments ending with Baseline hemodynamic parameters measurements.

d Dosing Period to occur over 6 hours from start to end of IV infusion (Hours 0 to 6).

e Postdose Period to occur over 18 to 24 hours from end of IV infusion (Hours 6 to 24 [+ 6 hours]).

f Subjects are discharged at the Investigator's discretion based upon clinical presentation (if the patient's clinical state allows) and after all scheduled assessments at Hour 24 (+ 6 hours) have been completed.

g Follow-Up phone contact to occur on Day 9 (± 2 days) to assess for AEs and any changes to concomitant medications. Site staff will work with Early Termination subjects to obtain as much follow-up data as possible.

h Assessments can occur within 60 minutes of Hour 6, with priority on the RHC assessments occurring as close as possible to 6 hours after start of IV infusion/EOI. The following order of assessments should be followed, if possible: 12-lead ECG, ECHO, vital signs, RHC hemodynamic parameter measurements, blood sampling, EOI, urine sampling.

-  Subjects who discontinue study treatment prior to the end of the full 6-hour IV infusion will immediately, if possible, complete the EEOI assessments followed by all Postdose Period/Follow-Up assessments. In such situations, order of assessments specified in footnote "h" can be modified, but the priority should be given to RHC hemodynamic parameter measurements, vital signs, and blood sampling occurring as close as possible to EOI.
- j Only weight. The weight collected during the Predose Period will be used to calculate the subject's dose.
- k Subjects are allowed a light meal 2 hours prior to RHC insertion (at least 4 hours prior to Baseline hemodynamic parameters measurements). Another light meal is provided after the 2-hour assessments are completed. After the end of RHC measurements, the meals can be provided per the site's SOC.
-  Physical examination is performed per the site's SOC at Screening and abbreviated physical examination is performed during the Predose Period. A symptom-based physical examination is performed prior to Discharge.
- m Vital signs include BP, HR, respiratory rate, and temperature. Temperature and respiratory rate are collected only at the following timepoints: Baseline, Hour 6, and Hour 24. During RHC assessments, vital signs (BP and HR) are collected within ± 5 minutes of hemodynamic parameter measurements.
- n If applicable, it is recommended to collect ECGs at least 30 minutes after the end of the subject's most recent meal.
- ECHO is performed at Screening to confirm eligibility (LVEF  $\leq$  35%).
- p RHC measurements for confirmation of hemodynamic eligibility criteria (CI  $\leq 2.5$  L/min/m^2 and PCWP  $\geq 15$  mm Hg) are performed at Baseline no less than 1 hour following RHC insertion. After at least 2-hour stabilization period, Baseline hemodynamic parameters measurements are performed prior to start of study treatment administration. During the Dosing and Postdose Periods, hemodynamic parameters measurements are performed at specified timepoints (at 0.5, 1, 2, 3, 4, 5, and 6 hours during Dosing Period, and at 0.5 and 1 hour during Postdose Period).
- q Cardiac biomarkers include NT-pro-BNP and hs-cTnT. Only cardiac troponin is required at Screening and Predose for eligibility purposes (hs-cTnT, hs-cTnI, cTnT, or cTnI), and it is collected and reported locally at Predose and at Screening if required per Section 10.3.5.
- r Renal function assessments include eGFR, BUN, cystatin C, urine protein/creatinine ratio, and urinary sodium excretion. Subjects are encouraged to provide urine sample at these timepoints. Only eGFR is required at Screening for eligibility purposes, and may be collected and reported locally if required per Section 10.3.4.
- s Urine output is assessed during prespecified intervals by having the subject empty his/her bladder and capturing the urine volume at indicated timepoints. Any spot urine samples collected during the intervals will be accounted for in the total volume for that specific interval. Urine output is assessed during the following intervals in relation to the start of the IV infusion: Baseline (within 2 hours prior to study treatment administration), every 2 hours during the IV infusion (at Hours 2, 4, and 6), and during the Postdose Period at 6 to 10 hours and 10 to 24 hours intervals.
- t Local laboratory assessments may be used for determining eligibility at Screening under certain circumstances; refer to Sections 10.2.8, and 10.2.9 for clinical laboratory assessments (and serum pregnancy) and urinalysis, respectively.
- u Serum pregnancy test is performed for female subjects of childbearing potential to determine eligibility at Screening. Urine pregnancy test is performed and a negative result is required to be documented for female subjects of childbearing potential at Day 1 prior to randomization to confirm eligibility. In case of positive urine pregnancy test, serum pregnancy test should be performed before the subject can be enrolled in the study.
- v It is not required to result the urine drug screen prior to randomization. If a urine drug screen cannot be obtained prior to study treatment administration due to the timing of events as required by subject safety considerations, then it can be obtained after study treatment administration and prior to discharge.
- w Continuous 6-hour IV infusion.
- x Blood samples for plasma PK are collected as denoted in the table above. In addition to the timepoints denoted in the table above, blood samples for plasma PK are collected during the Postdose Period at 6.083, 6.167, 6.25 hours. The collection at Hour 6 should be done within 10 minutes before EOI.
- y Urine samples for PK analysis are collected during the following intervals in relation to the start of the IV infusion: Baseline (within 2 hours prior to study treatment administration), 0 to 6 hours, 6 to 10 hours, and 10 to 24 hours.

AE, adverse event; BP, blood pressure; BUN, blood urea nitrogen; CI, cardiac index; DNA, deoxyribonucleic acid; ECHO, echocardiogram; ECG, electrocardiogram; EEOI, early end of infusion; eGFR, estimated glomerular filtration rate; EOI, end of infusion; HR, heart rate; hs-cTnT, high-sensitive cardiac troponin T; IV, intravenous; LVEF, left ventricular ejection fraction; NA, not applicable; N-pro-BNP, N-terminal pro b-type natriuretic peptide; PK, pharmacokinetic; PCWP, pulmonary capillary wedge pressure; RHC, right heart catheterization; SOC, standard of care; Tx, treatment

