## 6.3.1. Dose Interruptions

Dose interruptions should be avoided if possible. The IV infusion can be interrupted upon any sign of clinical concern or if a subject complains of pain, burning or stinging sensation at or around the insertion site or anywhere along the venous pathway. Prompt recognition and timely, appropriate action should be instituted to prevent any complication(s) and/or prolonging subject discomfort. If a mechanical issue (eg, occlusion or infiltration of IV lines) is identified or if the peripheral line is not well tolerated, the IV infusion site may be changed to another infusion site or a central line. The IV infusion may be interrupted to address these issues for up to 30 minutes. Following the interruption, the IV infusion should be resumed to complete the planned full

6 hours. However, in the event of an infusion site related AE, the subject may be discontinued from treatment at the discretion of the Investigator, as described in Section 10.6.1.

Subjects experiencing any type of infusion site AE should be closely observed for at least 24 hours after dosing or until symptom resolution, and should be clinically handled in accordance with the standard medical practice and relevant guidelines. At the conclusion of the Postdose in-clinic observation period, subjects who do not achieve complete symptom resolution but are improving and are stable for discharge should be instructed to monitor the affected area.

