## **11.6.** Study Endpoints

#### 11.6.1. **Primary Endpoint**

Change in CI measured by RHC from Baseline to end of IV infusion at 6 hours

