## 11.6.4. Exploratory Endpoints

Exploratory endpoints are:

- Change in hemodynamic parameters (measured by RHC) listed above at 1 hour after the end of 6-hour IV infusion (during Postdose Period)
- Change in vital sign, hemodynamic (measured by ECHO), and cardiac systolic function (measured by ECHO) parameters listed above for 18 hours after end of 6-hour IV infusion (during Postdose Period)
- The relationships between select APD418 plasma exposure measures and change in select PD parameters
- The relationships between select subject/disease characteristics (eg, Baseline LVEF, Baseline CI, Baseline SBP, duration of HFrEF, renal function, concomitant medications) and change in select PD parameters
- Change in markers of renal function (eGFR, BUN, cystatin C, urine protein/creatinine ratio, urinary sodium excretion)
- Change in cardiac biomarkers (NT-pro-BNP, hs-cTnT)
- Change in the following additional systolic and diastolic function parameters measured by ECHO: E, A, E', S', E/A E/E' ratio), TAPSE, tricuspid regurgitation (TR) velocity, and LA volume index
- Change in urine output
- Change in body weight
- The OATP genotype

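### Could a cardiac index taken after the infusion has stopped be recorded as the primary end-of-infusion value?

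*Combined protocol and SAP*

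**What the plan says.** Protocol Section 11.6.1 defines the primary endpoint as "Change in CI measured by RHC from Baseline to end of IV infusion at 6 hours".

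The timing of that reading is set in the footnotes to the Schedule of Assessments (Appendix 1, Table 4):

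- **Footnote h** allows Hour-6 assessments within "60 minutes of Hour 6, with priority on the RHC assessments occurring as close as possible to 6 hours after start of IV infusion/EOI". It continues: "The following order of assessments should be followed, if possible: 12-lead ECG, ECHO, vital signs, RHC hemodynamic parameter measurements, blood sampling, EOI, urine sampling".
- **Footnote d** bounds the period: "Dosing Period to occur over 6 hours from start to end of IV infusion (Hours 0 to 6").
- **Footnote p** lists the RHC readings: "at 0.5, 1, 2, 3, 4, 5, and 6 hours during Dosing Period, and at 0.5 and 1 hour during Postdose Period".
- **Footnote x** covers the Hour-6 pharmacokinetic (PK) sample: "The collection at Hour 6 should be done within 10 minutes before EOI".
- **Footnote i** covers early discontinuation. RHC is then done promptly around the stop, and the reading shares the Hour-6 column, which is headed 6/EEOI (early end of infusion).

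Sections 3.1 and 9.2 describe RHC through the infusion and then for one further hour after it ends. Section 11.6.4 makes the later reading exploratory: "Change in hemodynamic parameters (measured by RHC) listed above at 1 hour after the end of 6-hour IV infusion (during Postdose Period"). Section 10.3.1 defers RHC procedures to a core-lab manual. According to the biostatistics Note to File Addendum of 13 January 2023, the SAP stayed in draft. Neither the manual nor the draft SAP is among the supplied documents.

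**The concern.** Read alone, the 60 minutes in footnote h can run either way, from 5 to 7 hours. That span reaches the separate RHC readings at 5, 6.5 and 7 hours, of which the last two are post-dose. The order that puts RHC ahead of end of infusion is advisory. The PK draw has an explicit limit before end of infusion, and the primary CI has none.

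The stake would be dilution of the treatment effect. Section 1.4 reports that plasma levels fell rapidly once the infusion ended in healthy volunteers. If the CI effect fell with them, late readings labelled Hour 6 would understate it. One set of thermodilution recordings could also fit two nominal times with different endpoint status.

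Footnote h also names two anchors, 6 hours from start and end of infusion. Section 6.3.1 says "The IV infusion may be interrupted to address these issues for up to 30 minutes", so the two might separate.

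**Working it through.** **1. What a site following the schedule would do.** Footnote h lists RHC, then blood sampling, then end of infusion. Footnote x puts the blood draw in the last 10 minutes of the infusion. RHC done in that order therefore precedes a draw that itself precedes the stop. Footnotes p and d agree: the 6-hour reading belongs to the Dosing Period, which ends with the infusion. A CI at 6.5 or 7 hours entered as Hour 6 would go against the priority instruction and displace a reading scheduled for that time. What is left is a reading that slips by minutes.

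**2. The two anchors.** After an interruption, the infusion is resumed to complete the planned 6 hours.

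- If that means infusion time, it ends up to 30 minutes after clock Hour 6, and a CI at 6 hours from start is still on infusion.
- If it means clock time, the anchors coincide.

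Neither reading produces a post-infusion value.

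**3. The plan's own power figure.** Section 11.2 gives 20 per dose against 25 on placebo, difference 0.45, SD 0.5, two-sided 0.05.

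- Standard error = 0.5 × √(1/20 + 1/25) = 0.15.
- Noncentrality = 0.45/0.15 = 3.0, with 43 degrees of freedom.
- Power by noncentral t = 83.46%, which meets the stated minimum of 80%.

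Power reaches 80% at a mean effect of 0.430, which is 95.5% of 0.45.

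**4. Illustrated dilution.** Section 3.3 predicts a peak of 5700 ng/mL and a total AUC of 39,000 ng·h/mL at 12 mg/kg. For a one-compartment 6-hour infusion, AUC/Cmax = 6/(1 − e^(−6k)) = 39,000/5700 = 6.84. Hence k = 0.349 per hour and the half-life is 1.99 h. Concentration relative to end of infusion is r = e^(−kt): 0.971 at 5 minutes and 0.943 at 10 minutes. If effect is proportional to concentration and a share f of active-arm readings is late, the mean effect is d = 0.45 × [1 − f(1 − r)].

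| Share late | Delay | d | Power | Loss (points) |
|---|---|---|---|---|
| 10% | 5 min | 0.4487 | 83.25% | 0.21 |
| 10% | 10 min | 0.4475 | 83.04% | 0.42 |
| 25% | 5 min | 0.4468 | 82.93% | 0.53 |
| 25% | 10 min | 0.4436 | 82.41% | 1.05 |

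These are not bounds. Take a 10-minute delay with an assumed effect half-life of 1 h (r = 0.891) or 0.5 h (r = 0.794). With 25% late, power is 81.4% or 79.4%. If every active reading were late, it would be 74.3% or 64.3%, but that requires every site to disregard the footnote's order.

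**5. What a remedy would buy.** One option is a one-sided window of 30 minutes before the stop. It would accept readings from 5.5 h, which is looser than the present instruction to stay close to the end.

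Another is to set late values to missing. As complete-case worst cases at d = 0.45, before the repeated-measures model recovers anything:

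- 18 vs 25 (10% of active values lost): 81.13%.
- 15 vs 25 (25% of active values lost): 76.59%.
- 15 vs 19 (about 25% lost in both arms): 71.46%.

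With 25% late, keeping the values gives 82.41% in the table, and 79.4% even at the 0.5 h half-life. Both exceed 76.59%.

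A flag based only on whether the reading followed the stop would also catch the early-discontinuation readings of footnote i. It would mix treatment discontinuation with timing slippage, which are different analysis questions.

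**The case for a change.** The best case for a change is that intent is not a rule. The sponsor wrote a directional limit for the PK draw and none for the measurement behind the primary endpoint. PK is sampled at 6.083, 6.167 and 6.25 hours, so the schedule itself treats minutes after the stop as distinct. The one-compartment curve may also be too gentle for those first minutes: Section 11.6.3 lists a separate distribution half-life, and Section 1.4 describes a rapid fall. Writing a limit would cost one footnote.

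The textual part stands: the supplied documents contain no explicit limit before end of infusion for the Hour-6 CI. The caution about the curve stands too, which is why the power figures are only illustrations. But the fall in Section 1.4 is in plasma, in healthy volunteers. No passage links it to the offset of CI, and the PK Note to File Addendum says that the PK-PD analysis had not begun. The missing limit may already be in the core-lab manual or the draft SAP. Footnote h also already tells sites to do what the limit would require.

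**Conclusion.** This is a gap in wording that sites and analysts fill sensibly. Footnotes d, h, p and x read together put the Hour-6 CI on infusion, and the remaining exposure is a delay of minutes in some subjects. Under the proportional-effect assumption and the maximum-dose kinetics, the loss is 0.2 to 1.1 points from 83.46%. A faster offset would cost more, but the documents support no particular rate and give no share of late readings.

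No gain from a change has been shown. A main analysis that kept flagged values would barely move, and one that removed them could lose more precision than the dilution it avoids.

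The practical stake is also small. The biostatistics Note to File Addendum says that enrollment was terminated and that outputs cover Part A Cohort 1 (N = 7) and Cohort 2 (N = 15), 7 + 15 = 22 subjects. Its Appendix A lists individual RHC plots and Listing 16.2.6.1, with no repeated-measures output. Section 6.3 has the clock times of infusion start and end recorded. If RHC times were captured as well, which the supplied text does not state, an analyst can see which readings followed the stop without any amendment.
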